Intervention sessions are described in detail in the attached Appendix A (PRISM manual). They are scheduled approximately weekly to every-other-week, depending on participant preference to optimize feasibility and completion. Briefly, for each session, coaches (i) ensure a private video conference to enable participation and conversation; (ii) review session content and format; (iii) teach and practice a particular resilience skill; and (iv) plan opportunities to practice the skill. Session 1, Stress-Management, involves mini-skills such as deep breathing, guided imagery, and mindfulness. Session 2, Goal-Setting, involves deconstructing and reconstructing goals to make them “SMART” (Specific, Measurable, Actionable, Realistic, and Time-Dependent). The session also includes exercises to plan for challenges and alternative strategies. Session 3, Cognitive Restructuring, involves recognizing negative self-talk and reframing impressions of negative experiences to make them feel more manageable. Session 4, Meaning-Making, involves exercises to find gratitude and purpose in the context of adversities like cancer. Session 5 (optional), Coming Together, is optional and involves the participant and their loved ones discussing the program and lessons-learned. Session 6 (optional) involved advance care planning to discuss future goals related to medical care.

Throughout the program, participants will have access to the award-winning PRISM smartphone app. This program provides practice opportunities for all of the skills, plus an embedded journal to catalogue goals, lessons-learned, and gratitudes; a library of related, evidence-based resources; tracking tools to monitor one’s own stress and resilience.

The total PRISM intervention lasts 6-8 weeks, and the app is available thereafter, indefinitely.

3.4 Study Procedures-Surveys: Following enrollment, the participants will be asked to complete baseline surveys at the time of consent. The research coordinator will register the patient, providing the study ID, patient phone number, and email address for survey completion to the PRO Core team at the University of North Carolina. Surveys will be

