completed electronically, when possible, but paper and telephone-based options will be available for patients not able to complete electronically. Baseline surveys should be completed within 90 days of completion of definitive therapy (chemotherapy, radiation, or surgery) for Cohort 1 (early stage) and at any time post metastatic diagnosis for Cohort 2 (metastatic). We will allow people to enroll during ongoing maintenance therapy with non-cytotoxic therapies including endocrine therapy, targeted therapy (e.g. Her2-targeted therapy) or immunotherapy. Patients will be asked to complete a follow-up survey after completion of the PRISM intervention, with a goal completion of within 60 days. We will make up to 5 attempts to reach patients if they do not complete their survey. The survey includes 114 questions at baseline and 106 questions at follow-up on feasibility, acceptability, appropriateness, recent stressors, fear of recurrence, anxiety, depression, social determinants of health, spirituality, resilience, posttraumatic growth, patient activation, and quality of life (**Table 2**). The survey is expected to take approximately 30-40 minutes to complete.

Survey responses will be captured using a database hosted by the University of North Carolina PRO Core. The staff at PRO Core will contact participants once prior to each survey due-date, and up to 4 times thereafter for missed surveys. PRO Core will oversee data monitoring and quality. PRO Core adheres to best practices for data security and privacy. PRO Core is accessed through a web interface using a secure, authenticated login. Data are stored in a secure enterprise-level Oracle database; the databases and web servers are hosted by the UNC Center for Bioinformatics. Data transmitted between the server and end-users are encrypted using SSL, and all databases are encrypted. PRO Core will store patient data in a secure database identified by a coded study ID. Upon study conclusion, the de-identified dataset will be transferred to UAB via secure transfer and stored in a password protected file for analysis.

3.5 Study Procedures- Biological Specimens (Cohort 1 Early Stage Breast Cancer Patients Only):

Blood samples:

Blood samples will be collected at baseline and approximately 6 months after surgery (post PRISM intervention, aligned with standard of care appointment where possible).

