Nail sample collection and analysis: Cortisol measurements will also be derived from nail samples. Nail samples will be provided by participants using fingernail trimming clippers. They will be sent to the Bio-Analytical Redox Biology (BARB) Core at UAB for further analysis. Fingernails and toenails will be cut and stored independently until processed using the procedure previously described. Briefly, nail samples will be washed twice with 2 mL isopropanol and dried overnight. The dried nail samples will be added to a pre weighed tube containing three 5 mm steel grinding balls (Retsch) and ground using a TissueLyser II (Qiagen Venlo, Netherlands) at 30 Hz for 9 min. 1 mL of methanol will be added per 50 mg of powdered nail (w/v) and placed on a rotator for 18 h at room temperature to extract the cortisol. Samples were then centrifuged at 10,000 x g for 5 min. 800 μ L of supernatant was transferred to a clean tube and evaporated under nitrogen gas in a certified fume hood. The evaporated sample will be resuspended in 400 μ L of phosphate buffered saline per 50 mg of ground sample (w/v). Cortisol will be assayed using 25 μ L of sample according to manufacturer's protocol (Salimetrics, Salivary Cortisol Enzyme Immunoassay Kit, 1-3002, State College, PA).

3.5 Study Procedures- Intervention (Both Cohorts): Following baseline survey and biospecimen collection, participants will schedule their PRISM sessions with study staff, who will also connect them with their coach. Staff and coaches will verify best contact methods and confirm timelines with participants. Coaches will provide a calendar of sessions as appointments. Staff and/or coaches will provide session reminders via phone, email, and/or text, based on participant preference, one day and 15-minutes prior to each session.

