No formal power calculation is needed for this pilot study as feasibility is defined by patient participation and completion of surveys. Following NIH guidelines, no formal testing will be conducted. Uncertainty of pre-post change estimates will be measured with 95% confidence intervals. Assuming 70% completion in the full sample (N=40), a standardized outcome, and intra-subject correlation values 0.5, 0.6, and 0.7, the upperbound half-widths of 95% confidence intervals for pre-post change are 0.38, 0.35, and 0.30, respectively. These provide reasonable ranges for potential values of change that can be expected in a future project (computations in PASS 23 software).

3.9 *Biomarker evaluation:* Data from biomarkers and ePROs will be merged with demographic data using a study ID and date of collection. We will assess the relationship between biomarker outcomes and patient-reported outcomes. We will assess for correlational trends that would support evaluation in a larger cohort. We will examine distribution and ranges of biomarker data and determine whether variance stabilizing transformations are needed such as a natural logarithm, prior to analysis. As described above, we will employ a similar quantitative approach to compare pre/post intervention differences in assessed levels of cortisol, allostatic load, DAMPs and inflammatory response biomarkers (cytokines).

3.10 *Data linkage:* Both ePRO data and the data from biospecimens will be labeled using a Study ID. A separate tracking log will be kept with Study ID and MRN at UAB. This tracking log will be used to link datasets for analytic purposes.

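### The pre/post cortisol comparison makes no allowance for nail grow-out: toenail clippings, and many fingernail clippings, labelled 'post' would have formed before or early in PRISM

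*Combined protocol and SAP*

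**What the plan says.** Specimens are taken in Cohort 1 only. The nail paragraph of section 3.5 (Biological Specimens) says "Cortisol measurements will also be derived from nail samples", and "Fingernails and toenails will be cut and stored independently until processed". It describes washing, grinding, extraction and assay in detail. It gives no collection day, clip length or regrowth interval, and does not say what period a clipping represents. The blood paragraph of the same section adds serum cortisol at each draw.

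The timing statements are:

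- Section 3.5 (Intervention, Both Cohorts), on baseline specimens: "Following baseline survey and biospecimen collection, participants will schedule their PRISM sessions with study staff".
- Section 3.3, on programme length: "The total PRISM intervention lasts 6-8 weeks".
- Section 3.5, on follow-up specimens, for blood only: "Blood samples will be collected at baseline and approximately 6 months after surgery (post PRISM intervention", with routine appointments used where possible.
- Section 3.4, on the follow-up survey: "Patients will be asked to complete a follow-up survey after completion of the PRISM intervention, with a goal completion of within 60 days".
- Section 3.4, on the Cohort 1 baseline survey: "Baseline surveys should be completed within 90 days of completion of definitive therapy (chemotherapy, radiation, or surgery) for Cohort 1 (early stage".

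Section 3.9 then proposes to "compare pre/post intervention differences in assessed levels of cortisol, allostatic load, DAMPs" and cytokines, and to relate the biomarkers to the patient-reported outcomes. It does not say whether cortisol there means nail, serum or both, or which nail site is used.

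**The concern.** Serum cortisol describes the day of the draw. A nail clipping describes the period when that part of the nail was being formed, which lies in the past by the time it takes to grow out. If that time is longer than the gap between PRISM start and the follow-up clipping, the value labelled 'post' contains no exposure from during or after PRISM. With a 6-8 week programme the gap can be short.

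If the comparison in 3.9 is run on all clippings as written, some pre-PRISM cortisol will be reported as post-PRISM cortisol. The proportion will depend on each woman's surgery date, PRISM start and nail site. The correlation with follow-up (T2) survey scores would pair measurements from different periods, and nail and serum cortisol from the same visit would not measure the same thing. The study has one arm, so no control group would show that a nail change arose from timing alone.

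**Working it through.** The plan gives no figure for nail growth, so there is nothing to reproduce. The check is timing arithmetic.

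**Inputs from the documents**

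- PRISM length P: 6-8 weeks, i.e. 42-56 days (3.3).
- Survey goal: within 60 days of finishing PRISM (3.4). It is used here only as one possible nail date, because none is stated.
- Blood follow-up: about 6 months (182 days) after surgery (3.5).
- Cohort 1 baseline: within 90 days of completing definitive therapy (3.4, stated for surveys).

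**Assumptions not in the documents**

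- Root-to-clip lag L: 60-180 days for fingernail, about 365 days for toenail.
- A clipping contains about 30 days of growth.
- For the 6-month scenario, surgery is the last definitive therapy and PRISM starts at baseline, 0-90 days after surgery.

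**Formula.** With day 0 = PRISM start and T = day of the follow-up clipping, the clipping formed around day T - L.

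**Values of T**

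- Clipped at the end of PRISM: T = 42 to 56.
- Clipped 60 days later: T = 42 + 60 = 102 to 56 + 60 = 116.
- Clipped with the 6-month blood draw: T = 182 - 90 = 92 to 182 - 0 = 182.

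**Formation day, T - L**

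| Lag L (days) | End of PRISM | 60 days later | 6 months after surgery |
|---|---|---|---|
| 60 | -18 to -4 | +42 to +56 | +32 to +122 |
| 90 | -48 to -34 | +12 to +26 | +2 to +92 |
| 120 | -78 to -64 | -18 to -4 | -28 to +62 |
| 150 | -108 to -94 | -48 to -34 | -58 to +32 |
| 180 | -138 to -124 | -78 to -64 | -88 to +2 |
| 365 (toenail) | -323 to -309 | -263 to -249 | -273 to -183 |

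The fingernail ranges over all lags are therefore -138 to -4, -78 to +56, and -88 to +122.

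**Thresholds that do not depend on the assumed lag.** A clipping formed after PRISM start only if L < T. At the end of PRISM, any lag above 42-56 days fails. Sixty days later, any lag above 102-116 days fails. At the 6-month draw, the limit runs from 92 to 182 days depending on when PRISM began. A toenail would need a lag under 182 days even in the most favourable case. To form wholly after PRISM ended, L must be below T - P. That is 0 days at the end of PRISM and 60 days for the later clipping. At the 6-month draw it is 92 - 56 = 36 to 92 - 42 = 50 days for the later baseline, and 182 - 56 = 126 to 182 - 42 = 140 days for the earlier one.

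**Clip width.** Thirty days of growth spreads each value by 15 days either way. For example, T = 116 and L = 120 gives day -19 to +11, so 19/30 = 63% of the clipping predates PRISM. T = 182 and L = 120 gives day +47 to +77. With an 8-week programme, 9/30 = 30% of that formed during PRISM and 70% after it.

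**The case against.** A reader might infer that the nail comparison cannot show any change with PRISM. The documents do not support that. The 60-day goal belongs to the survey, and the only follow-up specimen time they give is the blood draw about 6 months after surgery. If nails follow that draw and PRISM starts near surgery (T = 182), fingernail lags of 90, 120 and 150 days place formation at day +92, +62 and +32, which is during or after PRISM. This part of the objection stands. However, that scenario is the favourable end of the range. With PRISM starting 90 days after surgery (T = 92), the same lags give day +2, -28 and -58. Scheduling delay after baseline, or definitive therapy continuing after surgery, would shorten T further.

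A reader might also infer that the nail value would track the end of cancer treatment, or that the plan will present it as the effect of PRISM. Neither is stated. Treatment dates vary, section 3.8 rules out formal tests, and section 3.9 looks for trends to support a larger study.

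Two further objections are fair. The growth lag comes from outside the documents, so the result is a range and not a finding about this assay. The plan also already holds most of what a correction needs: fingernails and toenails are stored apart, and biomarker data carry a collection date. But nothing in 3.9 uses either to decide which values enter the comparison.

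**Conclusion.** The concern holds as a problem of undefined and mixed exposure windows. Under the assumed lags, toenail clippings predate PRISM in every scenario, by 183 to 323 days. Fingernail clippings taken at the end of PRISM centre on a date before it started at every lag considered. Later fingernail clippings may reflect the time before, during or after PRISM, depending on the lag and on when the woman started. A single nail pre/post difference over all clippings would therefore have no consistent meaning and would not line up with serum cortisol or the T2 survey.

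This goes beyond missing detail, because following 3.9 as written would report some pre-PRISM cortisol as post-PRISM. Its reach is limited to nail cortisol, an exploratory measure in the 30 women of Cohort 1. Serum cortisol and the primary feasibility outcome are not touched. The conclusion rests on the assumed lags of 60-180 and about 365 days, and on the scheduling assumptions for the 6-month scenario.

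**What to change.** In section 3.9:

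- Name the cortisol source for each comparison. Report serum cortisol separately as the visit-day measure.
- Use fingernails only for any nail pre/post comparison.
- Fix a growth lag and clip width with the assay core before analysis, with a sensitivity range. Compute each clipping's formation window from its collection date and the date of the first PRISM session.
- Count a follow-up clipping as 'post' only if its window falls after PRISM start, and repeat the classification at both ends of the lag range.
- Report all other nail values, and all toenails, as earlier cortisol exposure.

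In section 3.5, state when the follow-up nails are to be collected relative to PRISM, and make sure the collection date and first session date are kept.

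It is not necessary to require a full lag after the last session. That would discard material formed during PRISM, which is relevant to change with the programme. Moving the clipping to a later date is possible, but it separates nails from the blood visit and survey and risks losing samples.

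The cost is a few sentences and one derived variable. The downside is fewer nail samples in the comparison, possibly very few if clippings are taken soon after PRISM.

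### Nail cortisol: a fixed 800 microlitre supernatant transfer between two mass-scaled volumes makes the assayed concentration inversely proportional to nail mass, and no correction is stated

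*Combined protocol and SAP*

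**What the plan says.** The nail procedure is in section 3.5 (Biological Specimens, Cohort 1 only), under nail sample collection and analysis. Its volumes, in order, are:

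- **Extraction, scaled to mass:** "1 mL of methanol will be added per 50 mg of powdered nail (w/v").
- **Transfer, not scaled:** 800 microlitres "of supernatant was transferred to a clean tube and evaporated under nitrogen gas".
- **Resuspension, scaled to mass:** "The evaporated sample will be resuspended in 400" microlitres of "phosphate buffered saline per 50 mg of ground sample (w/v").
- **Assay, fixed:** "Cortisol will be assayed using 25" microlitres of sample.

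The paragraph sets no target or minimum nail mass. It gives no reporting unit and no formula for turning the assay reading into cortisol per mg of nail. Fingernails and toenails are kept apart until processing, so one woman may contribute samples of different mass.

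Section 3.9 plans to "compare pre/post intervention differences in assessed levels of cortisol, allostatic load, DAMPs and inflammatory response biomarkers (cytokines") and to relate biomarkers to patient-reported outcomes. It provides for a variance-stabilising transformation but for no mass correction.

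**The concern.** Scaling both solvent volumes to mass is a sensible way to make readings comparable between samples of different weight. It works only if every step between them is on the same basis, and here the middle step is not. Two samples with the same cortisol per mg but different weights would then give different readings.

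Participants supply the clippings, and volumes stated per 50 mg suggest that mass is expected to vary. Biological measures of stress belong to the third study objective, and section 3.9 intends the correlations to justify work in a larger cohort. The study has a single arm, so if clippings were systematically heavier or lighter at the second collection, no control group would show that the apparent cortisol change came from weight. If mass varied without any trend, the effect would mainly be added noise in the change scores and in the correlations.

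**Working it through.** The plan states no figure to reproduce, so the check is a mass balance on the stated volumes.

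**Inputs from section 3.5:** 1 mL methanol per 50 mg; 0.8 mL supernatant transferred; 0.4 mL buffer per 50 mg.

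**Assumptions, not in the documents:** nail mass m of 50, 75 or 100 mg; true content c = 1 pg/mg. The value of c is only a unit and cancels from every ratio.

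**Steps, for m above 40 mg:**

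1. Methanol volume V = m/50 mL.
2. Extract concentration = c × m / (m/50) = 50c pg/mL, whatever the mass.
3. Amount in the aliquot = 0.8 × 50c = 40c pg, whatever the mass. This is the extract of 40 mg of nail.
4. Resuspension volume R = 0.4 × m/50 = 0.008m mL.
5. Assayed concentration C = 40c / (0.008m) = 5000c/m pg/mL.
6. Simple per-mg conversion = C × R / m = 40c/m pg/mg.
7. Aliquot fraction f = 0.8 / (m/50) = 40/m. Corrected conversion = C × R / (m × f) = c.

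| m (assumed, mg) | V (mL) | R (mL) | C (pg/mL) | Simple per mg (pg/mg) | f | Corrected (pg/mg) |
|---|---|---|---|---|---|---|
| 50 | 1.0 | 0.4 | 100 | 0.80 | 0.80 | 1.00 |
| 75 | 1.5 | 0.6 | 66.7 | 0.53 | 0.53 | 1.00 |
| 100 | 2.0 | 0.8 | 50 | 0.40 | 0.40 | 1.00 |

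Doubling the mass halves both the assayed concentration and the simple per-mg value, although the true content is the same in every row.

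**Log transformation.** ln C = ln(5000c) − ln m. The mass effect becomes an additive term and does not disappear. From 50 to 100 mg it is −ln 2 = −0.69.

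**Same basis at both steps:**

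- Fixed 0.8 mL into fixed 0.4 mL: 40c/0.4 = 100c pg/mL at every mass that yields the aliquot.
- Both per 50 mg: 50c × (0.8m/50) / (0.4m/50) = 100c pg/mL at every mass.

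**Lower limit of the fixed transfer.** V = m/50 reaches 0.8 mL at m = 40 mg. Below that, there is less than 800 microlitres of methanol and the step cannot be done as written. At exactly 40 mg the aliquot would be all the methanol added, which cannot realistically be drawn off the powder in full.

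**The case against.** The strongest reply is that the paragraph presents itself as a short account of a procedure described elsewhere. The centrifugation and transfer sentences are in the past tense within a mostly future-tense paragraph, as if condensed from an earlier methods text. The volumes fit together at 50 mg (1 mL of methanol, 0.8 mL taken, 0.4 mL of buffer), so 800 microlitres may be shorthand for a per-50-mg volume, or about 50 mg may be used every time. Either reading removes the problem. This possibility stands, but the protocol says neither, and its text as written puts the transfer on a different basis from the steps around it.

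A reader might infer that reported nail cortisol will be biased, so that a woman with unchanged cortisol who gives 50 mg and then 100 mg will be reported as having halved. The documents do not support that. The powder goes into a pre-weighed tube and methanol is added by mass, so mass should be known for each sample. With mass and volumes recorded, the true content is fully recoverable, as the last column of the table shows. The plan neither states nor excludes that calculation, and nothing shows that uncorrected concentrations would be analysed.

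Other limits also stand. The nail paragraph gives no collection times, and cortisol in section 3.9 could also mean serum cortisol, so a pre/post nail comparison is likely rather than explicit. Nail cortisol is exploratory, does not appear in Table 2, and is not subject to formal testing.

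**Conclusion.** The inconsistency is real. On the literal text, assayed concentration varies as 1/m for nails with identical cortisol content, and the obvious per-mg conversion leaves that dependence in place. This is certain for the assayed concentration and conditional for the value that will be analysed, which depends on a conversion the plan does not give.

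The 1/m relation needs only the stated volumes and a mass sufficient to yield the 800 microlitres. The size of any distortion in practice is unknown, because it depends on how far clipping mass varies between women and between collections. If every sample weighed the same, the relative effect would be nil.

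The consequence is confined to nail cortisol in the 30 Cohort 1 women: its change and its correlations with patient-reported outcomes. It should be settled before the assays are run, and it does not call the primary feasibility result into question.

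**What to change.** In the nail paragraph of section 3.5, adopt one of the following:

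- **Both volumes fixed:** 800 microlitres of supernatant into 400 microlitres of buffer for every sample.
- **Both volumes scaled:** 800 microlitres of supernatant and 400 microlitres of buffer, each per 50 mg.
- **Volumes as written, with the conversion stated:** cortisol per mg = C × R / (m × f), where f = 0.8/(m/50). With the written volumes this equals C × m/5000; for example, 50 × 100/5000 = 1.00 pg/mg.

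In every case, record the powder mass and the actual volumes for each sample, and name cortisol per mg of nail as the analysed quantity in section 3.9.

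If the fixed 800 microlitre transfer is kept, require a nail mass comfortably above 40 mg. For example, 50 mg gives 1 mL of methanol and leaves 0.2 mL with the powder. Alternatively, scale the aliquot for smaller samples and use the actual fraction transferred in the conversion. A threshold of exactly 40 mg would not work.

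The cost is a change of laboratory wording and one line in the analysis section, with no added burden on participants. A minimum mass may exclude some small samples, and scaling the aliquot avoids that loss. If the laboratory already applies the correction, stating it is enough.

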3.7 Compensation: Participants who complete biomarker and survey portions of the study will receive a \$50 gift card upon completion. Patients who complete the interview will receive an additional \$50 upon completion (\$100 total for Cohort 1, \$50 for Cohort 2).

3.8 Quantitative Analysis: Cohorts will be analyzed both separately and together. The primary outcome is feasibility, which will be defined as 70% of women completing all intervention components and 70% of survey time points (baseline, post-surgery, post intervention)

being completed. Secondary endpoints will include implementation outcome measures by Weiner, which will evaluate the acceptability, appropriateness, and feasibility (survey-based) of interventions.²⁰ Acceptability of Intervention Measure (AIM), Intervention Appropriateness Measure (IAM), and Feasibility of Intervention Measure (FIM) are implementation measures with four-items each, and a response scale ranging from 1 to 5 (1 = Completely disagree, 2 = Disagree, 3 = Neither agree nor disagree, 4 = Agree, 5 = Completely agree).²⁰ Scores for each measure are calculated by averaging responses.²⁰ An average of 4 or greater on each measure (AIM, IAM, FIM) will be considered acceptable, appropriate, and/or feasible.

We will also capture the following measures for future comparative efficacy trial:

- **Fear of recurrence** will be measured using the Fear of Cancer Recurrence Inventory Short Term (FCRI_SF) which is scored from 0 to 4 (0 = Not at all, 1 = A little, 2 = Somewhat, 3 = A lot, 4 = A great deal)¹³.
- **Patient depression** will be measured using the Patient Health Questionnaire depression scale¹⁴, which is a 2 questions screener with 6 additional questions for an 8 question scale with a cut-point of greater than or equal to 10 being defined as current depression.
- **Patient anxiety** will be measured using the General Anxiety Disorder-7 scale,¹⁵ which is a 7 item scale with scores of 0-4 signifying minimal anxiety, 5-9 mild anxiety, 10-14 moderate anxiety, and greater than 15 severe anxiety.
- **Resilience** using the Connor-Davidson Resilience scale which has 10 items each carry a 5 point range (0 = Not true at all, 1 = Rarely true, 2 = Sometimes true, 3 = Often true, and 4 = True nearly all of the time; total scores range from 0-40, and higher score indicate higher resilience)¹⁶

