- **Post-traumatic growth** will be measured using the Post-Traumatic Growth Inventory (PTGI), which is a 21 item questionnaire with each item scored from 0-5 with 5 being greater degree of change.¹⁷
- **Social determinants of health** will be measured using the CMS Health Related Social Needs, which is a 11 question survey.
- **Spirituality** will be measured using the FACIT-SP is 12 question instrument.
- **Patient activation** using the Patient Activation Measure scores of which range from 0 to 100 with four corresponding levels [level 1 (0.0 - 47.0), level 2 (47.1 – 55.1), level 3 (55.2 – 72.4), and level 4 (72.5 – 100) which indicates the highest level of activation]¹⁸;
- **Quality of life** using the PROMIS Global Scale which is a 10-item measure that is scored from 1 to 5 (1 = Never, 2 = Rarely, 3 = Sometimes, 4 = Often, 5 = Always).¹⁹ (Table 2)
- **Recent life stressors:** We will use a single open-ended questions asking “Have you had any additional life stressors in the last 3 months (in addition to your breast cancer diagnosis and treatment)?”

Descriptive survey statistics will be calculated using frequencies and percentages for categorical variables and medians and interquartile ranges for continuous variables. Data will be analyzed in aggregate, by race, by residence in high vs. low resource census blocks, and by presence of dependent children in the home. Pre-post changes in survey scores will be examined using mixed models repeated measures analysis with two points of data capture: surveys capturing data at baseline (T₁) and after PRISM intervention (T₂). Linear contrasts will be used to estimate average change in survey scores between timepoints and compute 95% confidence intervals. The modeling approach uses all available data. Patterns of missing data will be examined and if necessary, models will be

adjusted with covariates associated with missingness. Normality of residuals will be examined, and if found to be non-normal, generalized linear modeling will be used.

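### The survey half of the primary outcome counts the pre-PRISM baseline survey and sets no separate mark for the post-intervention survey, so read as a pooled percentage it can be met with follow-up well below 70%

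*Combined protocol and SAP*

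**What the plan says.** Section 3.8 (Quantitative Analysis) gives one primary outcome, feasibility, in two halves: "70% of women completing all intervention components and 70% of survey time points (baseline, post-surgery, post intervention") being completed. The survey half lists baseline as one of its time points. It does not say whether the 70% is taken over all surveys together, per woman, or at each time point.

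On timing, section 3.4 says "the participants will be asked to complete baseline surveys at the time of consent". Section 3.5 on the intervention puts baseline ahead of the programme: "Following baseline survey and biospecimen collection, participants will schedule their PRISM sessions with study staff".

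On the number of surveys, the rest of the protocol has two. Section 3.4 describes one later survey: "Patients will be asked to complete a follow-up survey after completion of the PRISM intervention, with a goal completion of within 60 days". It also gives content for two surveys only: "The survey includes 114 questions at baseline and 106 questions at follow-up". Table 2 has a baseline and a follow-up column, and the model in 3.8 is a "mixed models repeated measures analysis with two points of data capture: surveys capturing data at baseline" and after PRISM. The only collection tied to surgery is blood, in Cohort 1: "Blood samples will be collected at baseline and approximately 6 months after surgery".

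The precision statement at the end of 3.8 begins "Assuming 70% completion in the full sample (N=40") and reports half-widths of 0.38, 0.35 and 0.30 for pre-post change at within-subject correlations of 0.5, 0.6 and 0.7.

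**The concern.** A survey filled in at consent, before PRISM starts, says little about whether women stay engaged through the programme and report afterwards. If it counts equally with the follow-up survey in one percentage, a high baseline rate offsets a low follow-up rate, and the survey half of the primary outcome can be met when most women have given no post-PRISM data.

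Two other parts of the plan depend on the follow-up survey. AIM, IAM and FIM, the secondary endpoints, are collected only then (Table 2). The precision statement uses 70% completion to mean about 28 women with both measurements. A pooled survey criterion protects neither.

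**Working it through.** **Inputs.** N = 30 + 10 = 40 (section 3.1). Mark = 70% (3.8). Scheduled surveys: two (3.4, Table 2, mixed model); listed time points: three (3.8). Standardised outcome (SD 1) and correlations 0.5, 0.6, 0.7 (3.8). The protocol states no expected baseline completion rate, so b = 100% is an assumption and is varied below.

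**1. The plan's own figure.** With 70% of 40 = 28 complete pairs, half-width = t(0.975, n−1) × √(2(1−ρ)/n), and t(0.975, 27) = 2.052:

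| ρ | Computed, n = 28 | Stated |
|---|---|---|
| 0.5 | 0.388 | 0.38 |
| 0.6 | 0.347 | 0.35 |
| 0.7 | 0.300 | 0.30 |

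Two agree to two decimals and the first is about 2% off. The stated figures therefore correspond to about 28 women with both surveys.

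**2. Follow-up needed under pooling, two surveys.** Surveys due: 2 × 40 = 80. Needed: 0.70 × 80 = 56. With all 40 baselines in, 56 − 40 = 16 of 40 follow-ups (40%). By cohort: 42 − 30 = 12 of 30, and 14 − 10 = 4 of 10.

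In general the follow-up rate needed is 2 × 0.70 − b:

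| Baseline completion b (assumed) | Follow-up needed |
|---|---|
| 100% | 40% (16 of 40) |
| 95% | 45% (18 of 40) |
| 90% | 50% (20 of 40) |
| 80% | 60% (24 of 40) |

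**3. Follow-up needed under pooling, three time points as listed.** Surveys due: 3 × 40 = 120. Needed: 84. With 40 baselines, 44 of the 80 later surveys (55%). If all 40 post-surgery surveys were also returned, 84 − 80 = 4 of 40 post-intervention surveys (10%) would be enough. If only Cohort 1 had the third survey: 90 + 20 = 110 due, 77 needed, so 37 of 70 later surveys (53%).

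**4. Chance of meeting the survey half if the true follow-up rate were 50%** (illustrative rate; responses treated as independent):

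| Rule | Assumed baseline | Probability |
|---|---|---|
| Pooled, two surveys (56 of 80) | 100% | 0.92 |
| Pooled, two surveys | 95% | 0.77 |
| Pooled, two surveys | 90% | 0.56 |
| Pooled, three time points (84 of 120) | 100% | 0.22 |
| Post-intervention survey alone (28 of 40) | not used | 0.008 |

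The first row is P(Bin(40, 0.5) ≥ 16), the fourth P(Bin(80, 0.5) ≥ 44) and the last P(Bin(40, 0.5) ≥ 28). The second and third add a binomial baseline count. None includes the intervention half, so none is the probability that the primary outcome is met.

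**5. Precision with 16 follow-ups.** Complete pairs use the formula in step 1 with t(0.975, 15) = 2.131. Section 3.8 says the model uses all available data. With 40 baselines, n follow-ups and ignorable missingness, the variance of the estimated change is (1−ρ²)/n + (1−ρ)²/40. For ρ = 0.5 and n = 16 this is 0.75/16 + 0.25/40 = 0.0531, and 2.131 × √0.0531 = 0.49.

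| ρ | Stated | 16 complete pairs | 16 follow-ups, all available data |
|---|---|---|---|
| 0.5 | 0.38 | 0.53 | 0.49 |
| 0.6 | 0.35 | 0.48 | 0.45 |
| 0.7 | 0.30 | 0.41 | 0.39 |

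Using all available data, the intervals are about 30% wider than stated (0.49/0.38 = 1.29; 0.39/0.30 = 1.30).

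**The case against.** **Pooling is a reading, not a stated rule.** If the 70% is judged per woman, 1/2 and 2/3 both fall below 70%, so each counted woman needs every survey. If it is judged at each time point, follow-up itself needs 70%. Either reading removes the dilution. This stands. But the sentence speaks of time points being completed, which reads most naturally as one percentage, and readings that give 16 or 28 women on the two-survey schedule leave the primary definition unsettled.

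**Baseline may not be near 100%.** Women are asked to complete a 114-question survey, and section 3.4 provides for reminders when surveys are missed. No completion rate is given. This stands too, and it is why the figures are shown as a range.

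**A reader might infer that the 70% mark is reached with 40% follow-up as a matter of fact.** The documents do not support that without conditions. It needs two surveys, pooling and complete baseline, and the definition in 3.8 itself lists three time points, which gives 55%.

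**A reader might also infer that the trial will probably be declared feasible at 50% follow-up.** The 0.92 does not show this. It covers the survey half only, and 70% of women (28 of 40) must still complete all intervention components. That limits the problem but does not remove it, because finishing the sessions does not ensure that the survey is returned.

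**Low follow-up would be visible.** REDCap tracks each portion, missing-data patterns are examined, and women who do not complete surveys are invited to interview. In a pilot without formal testing, what goes into a feasibility benchmark is partly the investigators' choice, and the 70% in the precision statement is a planning assumption. All of this lowers the severity. None of it changes what the survey criterion can conclude.

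**Conclusion.** The point holds in conditional form. The survey half includes a pre-intervention survey and has no separate mark for the post-intervention one. Under pooling with complete baseline, the follow-up needed is 40% on the two-survey schedule; on the three listed time points, the later surveys must average 55%. Both are below the 70% that the precision statement assumes. The gap narrows as baseline completion falls, and it disappears under a per-woman or per-time-point reading. At the two-survey minimum, the pre-post intervals would be about 30% wider than stated, assuming SD 1 and ignorable missingness.

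This should be fixed, because it affects the primary conclusion and is cheap to correct. It does not undermine the design.

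**What to change.** In section 3.8, state the survey criterion as: at least 70% of all enrolled women, including any who are later replaced, complete the post-intervention survey. With 40 enrolled and none replaced that is 28, the number behind the plan's half-widths. Naming the denominator matters because section 3.1 replaces women who drop out without saying whether they still count.

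Report baseline completion separately. Report the proportion of follow-up surveys returned within the 60-day goal descriptively; the goal need not become a cut-off.

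In the same edit, reconcile the post-surgery time point in 3.8 with the two-survey schedule in 3.4, Table 2 and the mixed model: either remove it, or describe the survey and say which cohort receives it.

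The cost is a sentence or two, with no change to visits, procedures or sample size. The downside is that the criterion becomes harder to meet.
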